5.1.2. Statistical Methodology for Evaluation at the Final Analysis

All p-values below are one-sided p-values, to evaluate rejection of the null hypothesis that pimodivir is not better than placebo.

Scenario 1: The final analysis will be performed in the subgroup with time between onset of symptoms and start of treatment between 0 and 72 hours only. P-values for the final analysis will be based on 2 inverse-normal combination tests of p-values as outlined below.

Let:

- p = p-value (one-sided) from full study population of the pre-interim' category of the study period subgroup
- p_1 = p-value (one-sided) from subgroup with time between onset of symptoms and start treatment between 0 and 72 hours of the pre-interim' category of the study period subgroup
- p_2 = $2 * \min(p, p_1)$
- q_1 = p-value (one-sided), from subgroup with time between onset of symptoms and start treatment between 0 and 72 hours on the patients enrolled of the 'post-interim' category of the study period subgroup
- N_1 = actual sample size at interim i.e.:all randomized subjects analysis set (RAND) included in the IA
- N = 600, the initially planned study sample size
- w_1 = $\sqrt{N_1/N}$
- w_2 = $\sqrt{1-(N_1/N)}$
- $\phi^{-1}(x)$ = the inverse of the standard normal cumulative distribution function in x

Note: p_1 and q_1 are based on a subset of subjects with onset of symptoms and start treatment between 0 and 72 hours, and therefore this stratification factor is not included in the respective models.

The p-values resulting from the following 2 combination tests both should be below the pre-specified alpha (2.5% one-sided) to claim superiority in subgroup with time between onset of symptoms and start of treatment between 0 and 72 hours:

$$1-\phi(C(p_1, q_1)) \text{ where } C(p_1, q_1) = w_1 * \phi^{-1}(1-p_1) + w_2 * \phi^{-1}(1-q_1)$$

$$1-\phi(C(p_2, q_1)) \text{ where } C(p_2, q_1) = w_1 * \phi^{-1}(1-p_2) + w_2 * \phi^{-1}(1-q_1)$$

Scenario 2: The final analysis will be performed in the full study population. P-values for the final analysis will be based on 2 inverse-normal combination tests of p-values.

Let additionally:

- q = p-value from full study population on the patients enrolled of the 'post-interim' category of the study period subgroup

The p-values resulting from the following 2 combination tests both should be below the pre-specified alpha to claim superiority in the full study population:

$$1-\phi(C(p, q)) \text{ where } C(p, q) = w_1 * \phi^{-1}(1-p) + w_2 * \phi^{-1}(1-q)$$

$$1-\phi(C(p_2, q)) \text{ where } C(p_2, q) = w_1 * \phi^{-1}(1-p_2) + w_2 * \phi^{-1}(1-q)$$

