11.4. Efficacy Analyses

Descriptive statistics will be used for all efficacy endpoints and will be tabulated by treatment arm and stratification factors (baseline NEWS2, type of baseline SOC, and time since onset of influenza symptoms). Subgroup analyses will be performed by, but might not be limited to, treatment extension, region and age group.

As a confirmatory strategy, to account for multiplicity in the statistical evaluation of the most important efficacy endpoints, a combination of hierarchical testing and the Bonferroni-Holm testing procedure will be applied to control for the overall Type I error rate at the 5% level (2-sided). The following endpoints are included in the confirmatory strategy:

1. Hospital recovery scale at Day 6, ie, primary endpoint
2. Incidence in post-baseline complications
3. Time from start of study drug to hospital discharge
4. Time from ICU admission to ICU discharge
5. Time to return to daily activities
6. Time from start to end of mechanical ventilation
7. Rate of re-hospitalization

First, the primary endpoint will be tested for superiority of pimodivir in combination with SOC over placebo in combination with SOC at the 2-sided 5% significance level. If superiority is shown on the primary endpoint, then the 2 secondary endpoints indicated by 2. and 3. in the sequence above will be tested for superiority using the Bonferroni-Holm testing procedure: the smallest p-value from the analysis of these 2 secondary endpoints will be compared to a significance level of 0.025 and, if statistically significant (ie, 2-sided $p < 0.025$), then the 2-sided p-value for the second endpoint will be compared to a significance level of 0.05. If both endpoints show superiority, the same Bonferroni-Holm testing procedure will be applied to the 2 secondary endpoints indicated by 4. and 5. in the sequence above. If both these endpoints show superiority, the secondary endpoint indicated by 6. in the sequence above will be tested at the 2-sided 5% significance level. If superiority of this sixth endpoint is shown, the seventh and last endpoint in the sequence above will be tested at the 2-sided 5% significance level.

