5.1. Analysis Specifications

5.1.1. Level of Significance

The population used for the evaluation at the final analysis will depend on the outcome scenario of the interim analysis: i.e.; scenario 1: continue with the full study population or scenario 2: continue only with the subjects with an onset of symptoms less than 72 hours before first study drug intake. Tables/graphs/listings will account for the selected scenario.

As a confirmatory strategy, to account for multiplicity in the statistical evaluation of the most important efficacy endpoints, in either scenario, a combination of hierarchical testing and the Bonferroni-Holm testing procedure will be applied to control for the overall Type I error rate at the 5% level. The following endpoints are included in the confirmatory strategy:

1. Hospital recovery scale at Day 6, ie, primary endpoint
2. Incidence in post-baseline complications
3. Time to hospital discharge
4. Time from ICU admission to ICU discharge
5. Time to return to daily activities
6. Time from start of mechanical ventilation to end of mechanical ventilation
7. Rate of re-hospitalization

First, the primary endpoint will be tested for superiority of pimodivir in combination with SOC over placebo in combination with SOC at the 2-sided 5% significance level.

The confirmatory test procedure follows the Serial Gate Keeping strategy as outlined in Section 7 of the FDA's draft guidance on Multiple Endpoints to control the overall type I error at the 5% 2-sided level. The primary and six most important secondary endpoints (listed above) will be tested in the hierarchical order per the 5 steps outlined below. All alphas and p-values specified are 2-sided.

Step 1: Test the primary hypothesis ("Hospital recovery scale at Day 6")

- If the p-value is $\leq 5\%$, continue to Step 2.
- If the p-value is $> 5\%$, stop testing, and no claim will be made.

Step 2: Test first set of 2 secondary endpoints (“Incidence in post-baseline complications” and “Time from start of study drug to hospital discharge”). The Bonferroni-Holm procedure will be applied to control the type I error within Step 2.

- If the smallest of the 2 p-values is $\leq 2.5\%$ and the largest of the 2 p-values is $\leq 5\%$, continue to Step 3.

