- If the p-value is $> 5\%$, stop further testing of the secondary endpoints, and make a claim on “Hospital recovery scale at Day 6”, “Incidence in post-baseline complications”, “Time from start of study drug to hospital discharge”, “Time from ICU admission to ICU discharge”, and “Time to return to daily activities”.

Step 5: Test the sixth secondary endpoint (“Rate of re-hospitalization”)

- If the p-value is $\leq 5\%$, make a claim on “Hospital recovery scale at Day 6”, “Incidence in post-baseline complications”, “Time from start of study drug to hospital discharge”, “Time

from ICU admission to ICU discharge”, “Time to return to daily activities”, “Time from start to end of mechanical ventilation”, and “Rate of re-hospitalization”.

- If the p-value is >5%, make a claim on “Hospital recovery scale at Day 6”, “Incidence in post-baseline complications”, “Time from start of study drug to hospital discharge”, “Time from ICU admission to ICU discharge”, “Time to return to daily activities”, and “Time from start to end of mechanical ventilation”.

For the primary endpoint, the results from the proportional odds model will be used in the hypothesis testing. If the proportional odds assumption would not hold on the treatment effect, the p-value from the van Elteren test will be used. For the secondary endpoints time from start of study drug to hospital discharge, time from ICU admission to ICU discharge, time to return to daily activities, and time from start to end of mechanical ventilation, the results of the Gehan-Wilcoxon test will be used in the hypothesis testing. For incidence in post-baseline complications and rate of re-hospitalization the results of the logistic regression will be used. For all these evaluations p-value combination tests will be used, as described below.

The final analysis on the ITT-i set (to support FDA marketing approval) and the final analysis on the OST subset (to support marketing authorization approval in EMA) will be performed independently, using a 5% two-sided significance level for each.

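### SAP 5.1.2 prints one cut-off, 2.5% one-sided, for every combination p-value, but the first Holm test in Steps 2 and 3 needs 1.25% one-sided, and no sentence converts between the scales

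*SAP*

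**What the plan says.** SAP 5.1.1 sets out a five-step gatekeeping procedure and fixes its scale: "All alphas and p-values specified are 2-sided". Step 1 tests the primary endpoint for superiority "over placebo in combination with SOC at the 2-sided 5% significance level". Steps 2 and 3 each hold a pair of secondary endpoints tested by Bonferroni-Holm, with 2.5% for the smaller p-value and 5% for the larger. Steps 4 and 5 use 5%. Protocol 11.4 agrees on the Holm pairs: "the smallest p-value from the analysis of these 2 secondary endpoints will be compared to a significance level of 0.025 and, if statistically significant" (there marked as two-sided), "then the 2-sided p-value for the second endpoint will be compared to a significance level of 0.05".

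SAP 5.1.1 then says of the primary and all six secondary endpoints: "For all these evaluations p-value combination tests will be used, as described below". SAP 5.1.2 opens with "All p-values below are one-sided p-values". It defines two inverse-normal combination tests per endpoint and gives one numerical decision rule: the "combination tests both should be below the pre-specified alpha (2.5% one-sided) to claim superiority". That rule sits under Scenario 1 of 5.1.2 (≤72 h subgroup only). Scenario 2 (full population) refers to the same pre-set level without a number. I use the numbering of 5.1.2 throughout; 5.1.1 numbers the two scenarios the other way round.

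**The concern.** The figure 2.5% appears in both sections with different meanings. In 5.1.1 it is the two-sided level of the first Holm test. In 5.1.2 it is the one-sided equivalent of the overall 5% two-sided level. Neither 5.1.1 nor 5.1.2 gives 1.25% one-sided, says to double the combination p-value, or otherwise links the scales.

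A programmer who applies 5.1.2 as printed would test the smaller p-value of each Holm pair at 2.5% one-sided, which removes the Bonferroni split. The same data could then give different claims. Suppose the larger combination p-value is 0.02 one-sided for one endpoint of a pair and 0.03 for the other. Under 5.1.2 as printed, the first endpoint is claimed (0.02 < 0.025). Under 5.1.1, 2 × 0.02 = 0.04 exceeds 0.025, so neither is claimed. At stake is the stated control of the overall type I error for the secondary claims.

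**Working it through.** **Inputs.** Overall level 5% two-sided, Holm limits 2.5% and 5% two-sided (SAP 5.1.1, protocol 11.4). Cut-off 2.5% one-sided, planned N = 600, weights w1 = √(N1/600) and w2 = √(1 − N1/600), p2 = 2·min(p, p1) (SAP 5.1.2). Interim at N1 = 300 to 450 (SAP 3.1). At least 75% with onset ≤72 h (SAP 1.2); I use 75%. The correlation between the two endpoints of a pair is not given; I assume 0 to 0.7.

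**1. The plan's own figures.** One-sided 2.5% and two-sided 5% share the critical value 1.960, so the printed cut-off is right for the primary endpoint. The sample size also reproduces. Whitehead's formula with odds ratio 0.62 and the stated placebo distribution gives N = 12(1.960 + 1.282)² / [(ln 0.62)² × (1 − Σp̄³)] = 126.1 / (0.2285 × 0.917) ≈ 601, and 89.9% power at 600.

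**2. The level each test needs, one-sided.**

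| Test | Two-sided level in 5.1.1 | One-sided equivalent | Printed in 5.1.2 |
|---|---|---|---|
| Steps 1, 4, 5 | 5% | 2.5% (z = 1.960) | 2.5% |
| First Holm test, Steps 2 and 3 | 2.5% | 1.25% (z = 2.241) | 2.5% |
| Second Holm test, Steps 2 and 3 | 5% | 2.5% (z = 1.960) | 2.5% |

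Only the second row disagrees, by a factor of 2.

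**3. Error rate of the actual rule under the global null.** Each stage was simulated with independent standard normal statistics for the ≤72 h and later strata. The full-population statistic is √0.75 times the first plus √0.25 times the second. A claim requires both combination tests to pass. The table gives the one-sided chance of at least one false claim in a pair for the full-population scenario (2,000,000 runs per cell, assuming the step is reached).

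| Correlation | N1 | Cut-off 2.5% | Cut-off 1.25% |
|---|---|---|---|
| 0 | 300 | 3.04% | 1.52% |
| 0 | 450 | 2.97% | 1.48% |
| 0.3 | 300 | 2.95% | 1.48% |
| 0.3 | 450 | 2.91% | 1.47% |
| 0.5 | 300 | 2.82% | 1.43% |
| 0.5 | 450 | 2.79% | 1.42% |
| 0.7 | 300 | 2.58% | 1.31% |
| 0.7 | 450 | 2.58% | 1.32% |

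Further runs covering both scenarios put the ranges at 2.6–3.1% and 1.3–1.5%.

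**4. When the p2 test does not bind.** Suppose the ≤72 h subgroup benefits but the full-population null holds, which needs an offsetting adverse effect in the later stratum. Then p1 and hence p2 are small, the second combination test passes almost automatically, and only the test on (p, q) restrains a full-population claim. With one effective test per endpoint, the pair's error is 1 − P(Z1 < c, Z2 < c).

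- Correlation 0: 1 − 0.975² = 4.94% at 2.5%, and 1 − 0.9875² = 2.48% at 1.25%.
- Correlation 0.7: about 4.2% and 2.1–2.2%.

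**The case against.** The strongest reply is that 5.1.2 points back to a level fixed in advance, and that level can be read as the one for the step in question. On this view 5.1.1 and protocol 11.4 set the limits, 5.1.2 only says how each p-value is produced, and the parenthesis translates the overall 5% two-sided level. The first Holm test is then at 1.25% one-sided and error is controlled. This is a fair reading, and it means a doubled level is not established as the sponsor's intention. It does not remove the conflict: a fixed number is printed after every endpoint has been sent to that section, and it is the wrong number for one test in each pair.

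Three stronger inferences are not supported.

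- A reader might conclude that alpha is doubled at every step, by entering one-sided p-values directly against the 2.5% and 5% limits. The two-sided label in 5.1.1 rules this out, and so does the 2.5% one-sided cut-off in 5.1.2.
- A reader might take 4.2–4.9% as the general error rate of a pair. Those figures belong to one test per endpoint. The plan requires two to pass, which brings the rate to about 3% or less under the global null.
- A reader might say that the full-population scenario has no level. It refers to the same pre-set level, and 5.1.1 applies its procedure in either scenario; only the number is not repeated.

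**Conclusion.** The concern holds as an unresolved conflict in the confirmatory decision rule, confined to the first Holm test of Steps 2 and 3. Taken literally, the printed cut-off is twice the intended nominal level there. Under the global null the one-sided error per pair is then about 2.6–3.1% instead of 1.3–1.5%, so it passes 2.5% in every setting examined, by 0.1 to 0.6 percentage points. With 1.25% it stays below 2.5% throughout.

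These figures rest on 75% with onset ≤72 h, N1 of 300 to 450 and correlation 0 to 0.7. They also assume that the step is reached, so the unconditional rate is lower to the extent that earlier steps can fail.

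The 4.2–4.9% figure (against 2.1–2.5%) is best treated as an upper end. It needs benefit in ≤72 h subjects cancelled by harm in later ones, a pattern the interim analysis is meant to act on by stopping the later subgroup.

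The primary endpoint, its 5% two-sided test, the sample size and the power are unaffected.

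**What to change.** In SAP 5.1.2, for both scenarios, state that twice the larger of the two one-sided combination p-values (capped at 1) is the two-sided p-value entered in Steps 1–5 of 5.1.1. Equivalently, require both one-sided combination p-values to be at or below 1.25% at the first Holm test of Steps 2 and 3, and 2.5% elsewhere. Either wording should replace the parenthetical cut-off in Scenario 1 and the unnumbered level in Scenario 2.

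The cost is one sentence in the SAP, made before unblinding. It changes no design feature, sample size or data collection. Compared with the literal reading, it gives up only power that would have come from testing above the intended level.

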5.1.3. Data Handling Rules

For analysis purposes the \log_{10} qRT-PCR viral load will be imputed with 2.12 when the result is 'TARGET DETECTED' (.i.e. below the limit of quantification: <2.18) and with 2.05 if result is

‘TARGET NOT DETECTED’ (i.e. below limit of detection: <2.05). The \log_{10} TCID₅₀ viral titer will be imputed with 0.74 when the result is ‘ <0.75 ’ (below limit of quantification).

5.1.4. Stratification Factors

The actual values of the stratification factors will be used for all analyses.

The concomitant medications indicated as standard-of-care treatment on the concomitant medication form will be used for determining the actual strata for type of baseline SOC. If no influenza antiviral is recorded it will be assumed that the subject received SOC not including influenza antiviral. The following ATC level 4 code and generic medication names indicate an influenza antiviral:

- J05AH (including neuraminidase inhibitors)
- Laninamivir
- Umifenovir
- Amantadine
- Rimantadine
- Ribavirin
- Baloxavir Marboxil

The datetime when first acute respiratory symptoms appeared and the datetime of first dose of study drug will be used for determining the actual strata for time since symptom onset relative to treatment initiation.

The actual NEWS2 will be calculated as explained in Section 7.6. Note that a subject is considered to receive supplemental oxygen if the subject received oxygen according to the CM dataset at least at one point between 15 min before randomization date time to the randomization date time.

When an incorrect stratification occurred for the NEWS(2) such that the actual NEWS2 is lower than 4 or for the time to onset of symptoms to first study drug intake (i.e.: >96 hours) then use the randomized stratification category instead. Similarly, in case of missing data to calculate the actual NEWS2 stratification the randomized stratification factor will be used, except if the NEWS2 is greater or equal to 6 based on the available non-missing parameters, then the actual stratification will be ‘6 or more’.

There will be no missing stratification factors values for randomized subjects receiving study drug.

5.2. Primary Efficacy Endpoint(s)

5.2.1. Definition

The primary efficacy analysis will be based on the ITT-i analysis set and consists of the analysis of the hospital recovery scale outcome on Day 6.

The hospital recovery scale provides 6 mutually exclusive conditions ordered from best to worst, and the score reflects the subject’s worst situation on the day of assessment:

1. Not hospitalized
2. Non-ICU hospitalization, not requiring supplemental oxygen
3. Non-ICU hospitalization, requiring supplemental oxygen
4. Admitted to the ICU, not requiring invasive mechanical ventilation
5. Requiring invasive mechanical ventilation
6. Death

The hospital recovery scale categories are defined below. For ease of categorization, the categories are defined from worst to best. A subject will be evaluated in the same ordering of the categories as below. Once a subject fulfils the criteria for a category, the category is assigned to the subject and the evaluation stops.

6. Death

- Subject died at any time on the day of assessment or earlier (all-cause mortality).

5. Requiring invasive mechanical ventilation

- Any oxygen support requiring intubation or extracorporeal oxygenation
- Invasive mechanical ventilation is used at any time on the day of assessment.

4. Admitted to the ICU, not requiring invasive mechanical ventilation

Subject met either of the 2 following criteria:

- In the ICU (and ICU level of care is required during the day of assessment)
- On the hospital ward, with or without supplemental oxygen, but deemed to require ICU level of care at any time during the day of assessment (e.g., not transferred to ICU due to bed availability)

Requiring ICU level of care is defined by:

- Some specific conditions:
 - Treatment of acute unstable arrhythmias
 - Treatment of complicated acid-base or electrolyte imbalances
 - Large volume resuscitation
 - Utilization of intravenous vasoactive medications
 - S/P cardiac arrest
 - Cardiogenic Shock
 - Acute myocardial infarct with complications
 - Cardiac tamponade
 - Acute congestive heart failure
 - Acute or imminent respiratory failure
 - Hemodynamic instability

- Diabetic ketoacidosis complicated by hemodynamic instability, altered mental status, respiratory insufficiency, or severe acidosis
 - Other conditions requiring specialized equipment and/or staff competencies only available in the ICU
3. Non-ICU hospitalization, requiring supplemental oxygen

Subject met either of the 2 following criteria:

- Non-ICU hospitalized on the day of assessment (including readmittance), not ready for discharge during the whole day of assessment, as judged by the investigator and supplemental oxygen is required by the subject
- In the ICU but there is no medical reason to be in the ICU during the day of assessment, and supplemental oxygen is required by the subject

Requiring supplemental oxygen is defined by:

- Receiving supplemental oxygen through a face mask or nasal cannula and not being able to sustain a blood oxygen saturation of $\geq 94\%$ when breathing room air for 15 minutes at any time on the day of assessment.
- If supplemental oxygen was provided chronically pre-influenza infection (based on medical history), that amount of supplemental oxygen is exceeded to prevent hypoxia, tachypnea or dyspnea at some point on the day of assessment.
- Not receiving supplemental oxygen and either:
 - Having a blood oxygen saturation of $< 94\%$ when breathing room air for 15 minutes at any measurement on the day of assessment, or
 - In case of known pre-influenza $SpO_2 < 94\%$ (e.g., due to COPD), the current blood oxygen saturation on room air is lower than pre-influenza infection levels by at least 3%.

2. Non-ICU hospitalization, not requiring supplemental oxygen

Subject met either of the 2 following criteria:

- Non-ICU hospitalized on the day of assessment (including readmittance) and not ready for discharge during the whole day of assessment, as judged by the investigator
- In the ICU but there is no medical reason to be in the ICU during the day of assessment

1. Not hospitalized

Any of the following:

- Discharged from the hospital before the day of assessment
- Hospitalized at the day of assessment but ready for discharge on both the day of assessment and the day prior, as judged by the investigator (e.g., in case of lack of bed availability in a skilled nursing facility, lack of social support at home).

Notes: If a subject was discharged from the hospital “Against Medical Advice” on the day prior to the day of assessment, the subject will be considered as hospitalized (evaluating the other aspects of the HRS to define the correct category based on available data, e.g.: requiring supplemental oxygen, on the day of assessment). The hospital recovery scale category will be considered missing on subsequent days.

The HRS will be missing after a subject withdrew (except for withdrawal due to death) from the study.

See [Attachment 6](#) for details of the derivation of the HRS categories.

